12.6. Serology

12.6.1. Secondary serology analysis

12.6.1.1. (SO2) To evaluate the association between RSV-associated LRTI, RSVassociated severe LRTI and RSV neutralizing antibodies in the baseline cord blood samples collected from subjects, at birth.

Template 40 Seropositivity rate and geometric mean titres of [RSV-A – RSV-B] neutralising antibodies in the cord blood, Overall and by country (PPS)

		≥[8 – 6]			GMT					
				95% CI		95% CI				
Country	Ν	n	%	LL	UL	value	LL	UL	Min	Max
Overall										
Each Country										

GMT = geometric mean antibody titer calculated on PPS subjects

N = Total number of subjects with available results

n/% = number/percentage of subjects with titer equal to or above [8 - 6]

95% CI = 95% confidence interval; LL = lower limit, UL = upper limit

MIN/MAX = Minimum/Maximum

Template 41 Seropositivity rate and geometric mean titres of [RSV-A – RSV-B] neutralising antibodies by subjects classified according to nonoverlapping disease severity categories, in the first 3 months and 6 months of life, [Overall and by country] (PPS)

					[8 – 6]			GMT						
						95%	6 CI	95% CI						
Country	Age interval		Ν	n	%	LL	UL	value	LL	UL	Min	Max	Q1	Q3
	0-2 months	Non Case												
[Overall – by Country]		WHO RSV LRTI (excluding WHO RSV severe LRTI)												
		WHO RSV severe LRTI												
	0-5 months													

GMT = geometric mean antibody titer calculated on PPS subjects

N = Total number of subjects in the given category with available result (a subject is assigned to a single category based on the highest severity of the symptom experienced)

n/% = number/percentage of subjects with titer equal to or above [8 – 6]

95% CI = 95% confidence interval; LL = lower limit, UL = upper limit

MIN/MAX = Minimum/Maximum

Q1/Q3 = Quartile 1/Quartile 3

Note :

Non case is defined as subject not experiencing WHO RS V LRTI or WHO RSV severe LRTI in the given time interval An episode is confirmed as RSV positive using swab sample by qRT-PCR

200150 (EPI-RSV-005 BOD)

Statistical Analysis Plan Amendment 1 Final

Template 42 Seropositivity rate and geometric mean titres of [RSV-A – RSV-B] neutralising antibodies by subjects classified according to overlapping disease severity categories, in the first 3 months and 6 months of life, [Overall and by country] (PPS)

						[8 – 6]		GMT						
			9		95% CI			95% CI						
Country	Age interval		Ν	n	%	LL	UL	value	L	UL	Min	Max	Q1	Q3
	0-2 months	Non Case												
[Overall – by Country]		WHO RSV LRTI												
		WHO RSV severe LRTI												
	0-5 months													

GMT = geometric mean antibody titer calculated on PPS subjects

N = Total number of subjects in the given catoegory with available results

n/% = number/percentage of subjects with titer equal to or above [8 – 6]

95% CI = 95% confidence interval; LL = lower limit, UL = upper limit

MIN/MAX = Minimum/Maximum

Q1/Q3 = Quartile 1/Quartile 3

Note :

Non case is defined as subject not experiencing WHO RS V LRTI or WHO RSV severe LRTI in the given time interval An episode is confirmed as RSV positive using swab sample by qRT-PCR

There may have been multiple swabs for an episode. In such cases, the swab with highest viral load was considered for this analysis

Template 43 [Univariate – Multivariate] estimated coefficients for Cox models with RSV-A and RSV-B by seropostivity status, for first WHO [RSV-LRTI – RSV Severe LRTI] episode, over the follow-up period from [0-2 months – 0-5 months] (PPS)

Characteristics	Category	Number of				
		Observations		Hazard		.
		Used in the	Event		n value	Global p-
	O	model	Event	(95% CI)	p-value	value
levels in cord blood	Seronegative					
	Seropositive					
RSV-B maternal antibodies levels in cord blood	Seronegative					
	Seropositive					
Country	Argentina					
	Missing					
Gender	Female					
	Male					
	Missing					
	Within transmission					
Time of birth	season					
	Outside transmission					
	season					

200150 (EPI-RSV-005 BOD)

	Statistical Analysis Plan Amendment 1 Fina											
Characteristics	Category	Number of Observations Used in the model	Event	Hazard ratio (95% CI)	p-value	Global p- value						
Gestational age at birth	<= 36 weeks											
	>36 weeks											
Birth weight	< 2.5 kg											
	>= 2.5 kg											
Apgar at 5 mins of age	0-3											
	4 – 6											
	>= 7											
	Missing											
First degree relative with FH of	Yes											
asthma	No											
	Missing											
Highest education level of the	Yes											
mother: Higher education /	No											
university	Missing											
Highest education level of the	Yes											
father: Higher education /	No											
university	Missing											
Number of people living in the	1-3											
household at Month 3	4-6											
	>=7											
Number of other children (<18	0											
years old) living in the	1-2											
household at Month 3	>=3											
Subject in regular close contact	Yes											
with toddlers at Month 3	No											
	Missing											
The child live in a surrounding	Yes											
where people smoke daily at	No											
Month 3	Missing											
Breast feeding*	Yes											
_	No											
	Missing											

Hazard ratio (95% CI) = Hazard ratio and 95% confidence intervals

RSV-A seronegative samples are defined as samples with RSV-A maternal antibodies levels in cord blood < 8 RSV-B seronegative samples are defined as samples with RSV-B maternal antibodies levels in cord blood < 6 RSV-A seropositive samples are defined as samples with RSV-A maternal antibodies levels in cord blood >= 8 RSV-B seropositive samples are defined as samples with RSV-B maternal antibodies levels in cord blood >= 6 Subjects with missing cord blood value for RSV-A or RSV-B were excluded from this analysis

* Time-varying covariates :

- Number of observations used in the model = Number of observations which appeared at least once in the followup period. One observation can be counted in several modalities.
- Event = The number of events corresponds to the value recorded at the most recent visit before the endpoint.
- Event = The number of events corresponds to the value recorded at the most recent visit before the endpoint.

200150 (EPI-RSV-005 BOD)

Statistical Analysis Plan Amendment 1 Final

Template 44 [Univariate – Multivariate] estimated coefficients for Cox models with RSV-A and RSV-B as semi-quantitative variable by quartiles, for first WHO [RSV-LRTI – RSV Severe LRTI] episodes, over the followup period from [0-2 months – 0-5 months] (PPS)

Characteristics	Category	Number of				
		Observations		Hazard		
		Used in the		ratio		Global p-
		model	Event	(95% CI)	p-value	value
RSV-A maternal antibodies	Q1 (min - max)			,	-	
	Q2 (min - max)					
	Q3 (min - max)					
	Q4 (min - max)					
RSV-B maternal antibodies	O1 (min - max)					
levels in cord blood						
	Q2 (min - max)					
	Q3 (min - max)					
	Q4 (min - max)					
Country	Argentina					
	Missing					
Gender	Female					
	Male					
	Missing					
	Within transmission					
Time of birth	season					
	Outside transmission					
	season					
Gestational age at birth	<= 36 weeks					
	>36 weeks					
Birth weight	< 2.5 kg					
	>= 2.5 kg					
Apgar at 5 mins of age	0-3					
	4 – 6					
	>= 7					
	Missing					
First degree relative with FH of	Yes					
asthma	No					
	Missing					
Highest education level of the	Yes					
mother: Higher education /	No					
university	Missing					
Highest education level of the	Yes					
father: Higher education /	No					
university	Missing					
Number of people living in the	1-3					
household at Month 3	4-6					
	>=7					
Number of other children (<18	0					
vears old) living in the						
household at Month 3	>=3			+		}
	10	1	1	1	1	1

200150 (EPI-RSV-005 BOD)

	•	,
Statistical Ana	ysis Plan Amendmen	t 1 Final

Characteristics	Category	Number of Observations Used in the model	Event	Hazard ratio (95% CI)	p-value	Global p- value
Subject in regular close contact	Yes					
with toddlers at Month 3	No					
	Missing					
The child live in a surrounding	Yes					
where people smoke daily at	No					
Month 3	Missing					
Breast feeding*	Yes					
-	No					
	Missing					

Hazard ratio (95% CI) = Hazard ratio and 95% confidence intervals

Subjects with missing cord blood value for RSV-A or RSV-B were excluded from this analysis

* Time-varying covariates :

- Number of observations used in the model = Number of observations which appeared at least once in the followup period. One observation can be counted in several modalities.

- Event = The number of events corresponds to the value recorded at the most recent visit before the endpoint.

Template 45 [Univariate – Multivariate] estimated coefficients for Cox models with RSV-A and RSV-B as continuous variable, for first WHO [RSV-LRTI – RSV Severe LRTI] episodes, over the follow-up period from [0-2 months – 0-5 months] (PPS)

Characteristics	Category	Number of Observations Used in the model	Event	Hazard ratio (95% CI)	p-value	Global p- value
RSV-A maternal antibodies levels in cord blood	Continuous					
RSV-B maternal antibodies levels in cord blood	Continuous					
Country	Argentina					
	Missing					
Gender	Female					
	Male					
	Missing					
	Within transmission					
Time of birth	season					
	Outside transmission					
	season					
Gestational age at birth	<= 36 weeks					
	>36 weeks					
Birth weight	< 2.5 kg					
_	>= 2.5 kg					
Apgar at 5 mins of age	0-3					
	4 - 6					
	>= 7					
	Missing					

200150 (EPI-RSV-005 BOD) Statistical Analysis Plan Amendment 1 Final

		Statistic	al Ana	ilysis Pla	n Amename	nt i rinai
Characteristics	Category	Number of				
		Observations		Hazard		
		Used in the		ratio		Global p-
		model	Event	(95% CI)	p-value	value
First degree relative with FH of	Yes					
asthma	No					
	Missing					
Highest education level of the	Yes					
mother: Higher education / university	No					
	Missing					
Highest education level of the	Yes					
father: Higher education /	No					
university	Missing					
Number of people living in the	1-3					
household at Month 3	4-6					
	>=7					
Number of other children (<18	0					
years old) living in the	1-2					
household at Month 3	>=3					
Subject in regular close contact	Yes					
with toddlers at Month 3	No					
	Missing					
The child live in a surrounding	Yes					
where people smoke daily at	No					
Month 3	Missing					
Breast feeding*	Yes					
	No					
	Missing					

Hazard ratio (95% CI) = Hazard ratio and 95% confidence intervals

Subjects with missing cord blood value for RSV-A or RSV-B were excluded from this analysis

* Time-varying covariates :

- Number of observations used in the model = Number of observations which appeared at least once in the followup period. One observation can be counted in several modalities.

- Event = The number of events corresponds to the value recorded at the most recent visit before the endpoint.

200150 (EPI-RSV-005 BOD)

Statistical Analysis Plan Amendment 1 Final

Template 46 Descriptive statistics of total RSV viral load during first episode of WHO RSV LRTI episode by quartiles of [RSV A – RSV B] neutralizing antibody titres in cord blood in first 6 months of life, (PPS)

	Total Viral Load							
Quartiles of neutralizing antibody titers	n	Mean	95% Cl	SD	Q1	Median	Q3	Min/Max
Q1								
Q2								
Q3								
Q4								

n= Number of 1st episode within the quartile

SD=Standard Deviation

Q1 and Q3 = 1st and 3rd Quartiles

Min/Max = Minimum/Maximum

Total RSV viral load computed as RSV A Viral load + RSV B Viral load

Note:

An episode is confirmed as RSV positive using swab sample by qRT-PCR

There may have been multiple swabs for an episode. In such cases, the swab with highest viral load was considered for this analysis

12.6.1.2. (SO3) To determine the level of RSV antibody at 2, 4, 6, 12, 18 and 24 months in a randomly selected sub-cohort of subjects.

Template 47 Seropositivity rate and geometric mean titres of [RSV-A – RSV-B] neutralising antibodies by timepoint, Overall (PPS – sub cohorts)

		≥[8-6]	≥[8 – 6]			GMT				
				95% CI			95% CI			
Time point (Month)	Ν	n	%	LL	UL	value	LL	UL	Min	Max
0										
2										
4										
6										
12										
18										
24										

GMT = geometric mean antibody titer calculated on PPS sub-cohorts subjects

N = Number of subjects with available results at both baseline and sampling timepoint

n/% = number/percentage of subjects with titer equal to or above [8 – 6]

95% CI = 95% confidence interval; LL = lower limit, UL = upper limit

MIN/MAX = Minimum/Maximum

Note: Blood draw at month 0 is from cord blood sample

Note: Subjects that have no available result for randomized timepoints are not included in analysis of timepoint 0

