6.7.3. Laboratory assays

Please refer to APPENDIX A for a detailed description of the assays performed in the study. Please refer to APPENDIX C for the address of the clinical laboratories used for sample analysis.

The samples collected will be shipped to the study reference laboratory for testing.

The following assays will be performed at GSK Biologicals' laboratory or in a laboratory designated by GSK Biologicals using standardized and validated procedures.

For cord blood and sub-cohort blood samples:

• Serum neutralization assay to assess RSV antibody [Table 10].

Table 10 Antibody determination

System	Component	Method	Kit/ Manufacturer	Unit	Cut-off**	Laboratory
Serum	Anti-RSV-A	Neutralization	In house	ED60	8	GSK Biologicals* and/or designated laboratory
Serum	Anti-RSV-B	Neutralization	In house	ED60	6	GSK Biologicals* and/or designated laboratory

*GlaxoSmithKline Biologicals laboratory refers to the Clinical Laboratory Sciences (CLS) in Rixensart, Belgium; Wavre, Belgium.

** Unit and cut-off for the RSV-A and/or RSV-B neutralization assay may be subject to change RSV = Respiratory Syncytial Virus; ED = Effective Dose

For nasal swab samples:

- **RT-qPCR assay** for the detection of RSV and determination of RSV subtype (A/B).
- **xTAGTM RVP Fast assay** for the detection of the following 17 viruses and subtypes.
 - RSV
 - Influenza A, including subtypes H1 and H3
 - Influenza A H1N1 2009
 - Influenza B
 - Parainfluenza virus type 1, 2, 3, and 4
 - Human Metapneumovirus
 - Enterovirus/Rhinovirus
 - Adenovirus
 - Bocavirus
 - Coronavirus 229E, OC43, NL63, HKU1

The GSK Biologicals' clinical laboratories have established a Quality System supported by procedures. The activities of GSK Biologicals' clinical laboratories are audited regularly for quality assessment by an internal (Sponsor-dependent) but laboratoryindependent Quality Department.

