6.1.2. RSV

Geometric means and positivity status for RSV viral loads will be derived according to the following table:

Component	Raw result	Derivation for GM calculation	Derivation for positivity status
RSV-A	<llod< td="">LLOD /2	NEG	</llod<>	LLOD /2	NEG
	≥ LLOD	Exact value	POS
RSV-B	< LLOD	LLOD /2	NEG
	≥ LLOD	Exact value	POS

Table 5Derivation rule for GMT calculation of RSV viral load

The thresholds used for the derivation are detailed in the following table:

Table 6 Derivation rule for positivity status of RSV viral load

Component	Method	Unit	LOD
RSV-A	RT-qPCR	copies of RSV RNA per mL	1123
RSV-B	RT-qPCR	copies of RSV RNA per mL	1467

The subject will be considered to be RSV positive when the RSV infection will be confirmed on nasal swab by quantitative polymerase chain reaction (PCR) using both RSV-A (fields [LABO_RES.COMPONEN] = "RSV-A" and [LABO_RES.METHOD] = "QRTPCR" and [LABO_RES.RAWRES]) and RSV-B (field [LABO_RES.COMPONEN] = "RSV-B" and [LABO_RES.METHOD] = "QRTPCR" and [LABO_RES.RAWRES]) tests.

The subject will be considered as positive if one or both tests are positive.

A RSV-A test will be considered:

- Positive if [LABO_RES.RAWRES] \geq 1123 copies/ml
- Negative if [LABO_RES.RAWRES] < 1123 copies/ml

A RSV-B test will be considered

- Positive if $[LABO_RES.RAWRES] \ge 1467$ copies/ml
- Negative if [LABO_RES.RAWRES] < 1467 copies/ml

Please note that the RSV01 test will not be considered to derive RSV status for primary objectives.

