6.9. Neutralizing antibodies over time and protection against RSV disease analysis

6.9.1. Analysis of secondary objective: Association between RSV disease and cord blood neutralizing antibodies

The analysis will be based on PPS and will be done considering the 2 age intervals:

- 0-2 months
- 0-5 months

The analysis will be realized only on the first episode (and not recurrent events) occurring during the considered age interval using a stepwise approach.

Step 1: Descriptive analysis:

Descriptive analyses (seropositivity rate with 95% CIs, geometric mean, median, min, max) of RSV neutralizing antibodies in the baseline cord blood samples will be presented by WHO RSV LRTI and WHO RSV severe LRTI case status; and with overlapping and non-overlapping disease severity.

In addition, descriptive analyses (seropositivity rate with 95% CIs, geometric mean, median, min, max) of RSV neutralizing antibodies in the baseline cord blood samples will be analysed according to the following endpoints:

- All RSV positive nasal swab samples (see details 6.1.2)
 - WHO RSV LRTI
 - WHO RSV LRTI (excluding WHO RSV severe LRTI)
 - WHO RSV severe LRTI
- Descriptive analyses (mean, median, min, max) of the total viral load of RSV according to the quartiles of neutralizing antibodies detected in the cord blood will be described.

Step 2: Cox models:

The impact of the level of RSV neutralizing antibodies in the baseline cord blood samples on the incidence of first event of WHO RSV-LRTI and WHO RSV-severe LRTI separately will be assessed through Cox models.

Univariate and multivariable Cox models will be presented. The following covariates may be considered in the multivariable model

- General:
 - Country of birth
 - Gender
 - Time of birth relative to the transmission season
- Characteristics at birth:
 - Gestational age at birth
 - Birth weight
 - Apgar at 5 mins of age
 - Caesarian section
- Family history:
 - First degree relative with family history of asthma

Statistical Analysis Plan Amendment 1 Final

- Living environment and household composition:
 - Highest education level of the mother
 - Highest education level of the father
 - Number of people living in the household at month 3
 - Number of other children (<18 years old) living in the household at month 3
 - Subject in regular close contact with toddlers at month 3
 - The child live in a surrounding where people smoke daily at month 3
 - Breast feeding *

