* Time dependent covariate; status is yes of subject ever breastfed from DOB until the end of breastfeeding given in the surveillance visit. Last day of month will be imputed for any partial date of breastfeeding end date.

Covariates with univariate p-value less than 0.1 will be included in the multivariable model. The number of covariates included in the model will depend on the number of events (at least 10 events per covariates).

Please note that the multivariable model will be performed only if the number of events is sufficient (at least 10 events per covariates). In addition, depending on the data other models could be explored or the model could be simplified.

Step 2-a: RSV neutralizing antibodies classified as a binary variable: Seropositive and seronegative:

In a first step, the RSV neutralizing antibodies in the baseline cord blood samples will be introduced in the model as binary variable. If the effect of RSV neutralizing antibodies as binary variable is significant we process to the next step.

Step 2-b: RSV neutralizing antibodies classified as semi-quantitative variable: Ouartiles

In a second step, the RSV neutralizing antibodies levels will be introduce in the model using quartiles. And the Cox models will be performed as describe in the previous paragraph (RSV neutralizing antibodies as quantitative variable – Step 2-a). If the effect of neutralizing antibodies as semi quantitative variable is significant, we proceed to next step.

Step 2-c: RSV neutralizing antibodies classified as continuous variable:

In a third step, the RSV neutralizing antibodies levels might be treated as continuous variable in Cox models to evaluate how each unit of neutralizing antibody level change impacts on the above clinical outcomes. The Cox models will be performed as describe in the previous section (with log of RSV neutralizing antibodies as quantitative variable). For the subjects with antibody level below the LLOQ, a value of LLOD/2 will be imputed.

Note that depending on the results, a quantitative association between RSV-associated LRTI, RSV-associated severe LRTI and RSV neutralizing antibodies in the baseline cord blood samples could be further explored and described more in details in a separate Additional Analysis Request.

6.9.2. Analysis of secondary objective: prevalence of RSV infection at 2, 4, 6, 12, 18 and 24 months

The analysis will be based on PPS sub-cohort for this objective.

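### SAP 6.9.1 leaves open whether the RSV-A and RSV-B cord titres share an adjusted Cox model; if they do, as Templates 43–45 suggest, a shared protective effect is split and can be non-significant in both rows

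*SAP*

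**What the plan says.** The objective (SAP 3.2) concerns the association of cord-blood RSV neutralizing antibody with RSV LRTI and severe LRTI. On RSV status, SAP 6.1.2 pools the subtypes: "The subject will be considered as positive if one or both tests are positive".

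SAP 6.9.1 Step 2 says "Univariate and multivariable Cox models will be presented", screens with "Covariates with univariate p-value less than 0.1 will be included in the multivariable model", and requires at least 10 events per covariate. The antibody is coded in three steps. At the first, "the RSV neutralizing antibodies in the baseline cord blood samples will be introduced in the model as binary variable"; then "If the effect of RSV neutralizing antibodies as binary variable is significant we process to the next step", which is quartiles, followed by continuous log titre under a similar condition. The text does not say whether the two titres are fitted together, nor which titre or model is read at the gate.

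The layout appears only in SAP 12.6.1.1, Templates 43–45. Their titles name RSV-A and RSV-B together, as in "estimated coefficients for Cox models with RSV-A and RSV-B as continuous variable". Both titres are rows of one table, and a footnote states "Subjects with missing cord blood value for RSV-A or RSV-B were excluded from this analysis". Elsewhere (Templates 40–42, 46 and 47) the SAP puts RSV-A and RSV-B in square brackets to mark separate runs. The titles of Templates 43–45 use such brackets for the univariate and multivariate versions, the two endpoints and the two age windows, but not for the titres. Table 15 also lists RSV-A and RSV-B quartiles as two covariates.

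**The concern.** Both titres are measured on the same cord sample and plausibly mark the same maternal protection. With both in the model, the RSV-A row asks whether the A titre adds anything at a fixed B titre, and the RSV-B row asks the reverse. Neither row answers whether cord antibody is associated with RSV LRTI. If the titres are strongly correlated, the shared effect is divided between two imprecise coefficients, and both may be non-significant although either alone would be clear.

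Two things follow if the joint model is used. The step gate could stop before the quartile and continuous analyses. And quartiles of two titres use 6 model terms instead of 3; if the events rule counts terms, 77 events allow only 7. No joint test of the two titres, adjusted model per titre, combined titre or subtype-matched outcome is specified.

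**Working it through.** **1. The plan's own figure.** Protocol 9.3: 1920 evaluable children with 20% drop-out gives 1920/0.80 = 2400, as stated. The documents give no power, effect size or event count for the cord-antibody models.

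**2. Events from the protocol's rates.** Protocol 9.3 gives RSV LRTI hospitalisation rates of 16.9 to 44.1 per 1000 child-years under 6 months, uses 20 per 1000 as an example rate for the first year, and expects RSV LRTI at 8 times the hospitalisation rate. For 1920 children followed for 0.5 year:
- 1920 × 0.5 × 0.0169 × 8 = 130
- 1920 × 0.5 × 0.020 × 8 = 154 (half of this, 77, at 0–2 months)
- 1920 × 0.5 × 0.0441 × 8 = 339

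These are approximate: drop-out is spread over the whole follow-up, so with up to 2400 children at these ages the range would be about 162 to 423.

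**3. Assumptions, not in the documents.** Standardised log titres with correlation r; an effect shared equally by both titres; a hazard ratio of 0.75 per SD when one titre is fitted alone; two-sided 5% tests; no other covariates.

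**4. Formulas.** With D events and m = ln 0.75 = −0.288:
- One titre alone: power = Φ(√D·|m| − 1.96).
- Each titre adjusted for the other: coefficient b = m/(1 + r), power = Φ(√(D(1 − r²))·|b| − 1.96).
- Both rows non-significant: bivariate normal for the two test statistics, correlation −r.
- 2-df joint test: noncentral chi-square with noncentrality 2D·b²(1 + r).

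Example, D = 154 and r = 0.8: b = −0.288/1.8 = −0.160; √(154 × 0.36) = 7.45; 7.45 × 0.160 = 1.19; power = Φ(1.19 − 1.96) = 22%.

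**5. Results for 154 events** (one titre alone: 95% throughout)

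| r | HR expected in each adjusted row | Power per row | Both rows non-significant | 2-df joint test |
|---|---|---|---|---|
| 0 | 0.75 | 95% | 0.3% | 99.7% |
| 0.3 | 0.80 | 75% | 4% | 98% |
| 0.5 | 0.83 | 54% | 13% | 97% |
| 0.7 | 0.84 | 32% | 37% | 94% |
| 0.8 | 0.85 | 22% | 56% | 93% |
| 0.9 | 0.86 | 13% | 75% | 92% |
| 0.95 | 0.86 | 8% | 84% | 91% |

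Simulated Cox fits (1920 children, 0.5 year, 300 replicates per setting) agree: both rows were non-significant in 55%, 70% and 85% of runs at r = 0.8, 0.9 and 0.95. At r = 0.9, 65% of runs had each titre significant alone and neither significant together.

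**6. Sensitivity to event count.** Both rows non-significant at r = 0.5, 0.8 and 0.9: 42%, 74% and 83% with 77 events; 0.2%, 20% and 54% with 339 events. With 339 events, power per row is 97% at r = 0.3 and 86% at r = 0.5, against nearly 100% alone, so the losses are about 3 and 14 points.

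**7. If each titre protects only against its own subtype.** With an assumed hazard ratio of 0.70 per SD against the matching subtype and equal A and B frequency (about 154 events), the adjusted hazard ratios dilute to about 0.84–0.86. Both rows are non-significant in 20%, 50% and 66% of runs at r = 0.5, 0.8 and 0.9.

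**The case against.** A reader might infer that the SAP prescribes a joint fit. It does not. Section 6.9.1 lists the covariates that may be considered, and the other subtype's titre is not among them. Rows in a shell can be a menu of candidates: Template 17 lists binary, quartile and continuous codings of the same titres, which cannot sensibly all enter one model. The missing-titre footnote also covers the univariate version, so it may only fix a common sample. This objection stands: joint entry is the natural reading of the layout, not a stated rule.

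A reader might also infer that a real effect would vanish from the report. That goes too far. The univariate Cox models show each titre alone, Templates 41 and 42 give geometric mean titres by case status, and 6.9.1 foresees further quantitative work. What may be missing is an adjusted hazard ratio for each titre on its own. Nor do the adjusted estimates go to 1: under the shared-effect assumption they are expected near 0.83–0.86 for r between 0.5 and 0.95, with wide intervals.

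A large loss at every correlation is not supported either, as step 6 shows. The figures apply to the continuous coding, which is reached last; the binary coding was not computed.

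SAP section 7 calls the analyses descriptive and disclaims hypothesis testing. That lowers the stakes but does not remove them, since 6.9.1 itself uses a p-value screen and a significance gate. Mutual adjustment is also a fair question in its own right, namely which subtype's antibody carries the association, so it need not be banned.

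**Conclusion.** The point holds as an ambiguity in 6.9.1 that the shells resolve in the less useful direction. If both titres are entered together, the adjusted rows do not answer the secondary objective. With 154 events and a shared hazard ratio of 0.75 per SD, power per row falls from 95% to about 54%, 22% and 13% at r = 0.5, 0.8 and 0.9, while a 2-df joint test keeps 97%, 93% and 92%.

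The size rests on the assumed effect and on a correlation the documents do not give; it is small at low correlation with many events. It also does not carry over to severe LRTI. If severe cases are about as frequent as hospitalisations (1920 × 0.5 × 0.020 = 19), one titre alone has only 24% power, and the events rule would allow a single covariate. This is a worthwhile, inexpensive improvement, not evidence that the objective is lost.

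**What to change.** In SAP 6.9.1 and Templates 43–45:

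- Make one adjusted Cox model per titre, with the same other covariates, the main result.
- Add a 2-df likelihood-ratio test of RSV-A and RSV-B together as the overall answer to the objective. This needs both titres in one model, so a mutually adjusted model may stay if labelled supplementary.
- State which titre, model and test decide the moves from binary to quartile to continuous coding.
- As support, relate A titre to first RSV-A LRTI and B titre to first RSV-B LRTI, using the subtype already determined by RT-qPCR (Protocol 6.7.3).
- Bring Table 15 and Template 17 into line.

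The cost is SAP wording, a few more model runs and extra tables. No new data are needed. The subtype-matched analysis will have fewer events per model.
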